¹¹¹In-XYIMSR-01. In 2015 Wichert and co-workers identified a promising dual-motif inhibitor of CAIX from a DNA-encoded chemical [25]. We subsequently improved upon this agent by replacing the IRDye750 portion of their molecule with the hydrophilic species 1,4,7,10-tetraazacyclododecane-1,4,7,10-tetraacetic acid (DOTA), which enables convenient radiolabeling with metal isotopes for positron emission tomography (PET), single photon emission computed tomography (SPECT), and radiopharmaceutical therapy [26, 27]. We have termed this agent XYIMSR-01 have previously reported our pre-clinical experience with an indium-111 labeled (¹¹¹In) version of the molecule [27]. SPECT imaging of immunocompromised mice bearing CAIX-expressing SK-RC-52 tumors revealed radiotracer uptake in tumor as early as 1 hour post-injection. Biodistribution studies demonstrated 26% injected dose per gram of radioactivity within tumor at 1 hour. At 24 hours post-injection, Tumor-to- blood, muscle, and kidney, ratios were 178.1 ± 145.4 , 68.4 ± 29.0 and 1.7 ± 1.2 , respectively. Retention of radioactivity was exclusively

observed in tumors by 48 hours, the latest time point evaluated. In total, imaging with ^{111}In -XYIMSR-01 enabled specific detection of ccRCC in this xenograft model, with pharmacokinetics surpassing those of previously described radionuclide-based probes against CAIX.

Dosimetry. Using the biodistribution data generated in the paper by Yang et al. we have estimated the human dosimetry for ^{111}In -XYIMSR-01 agent.

Target Organs	Organ Dose (rem/mCi)	Organ Dose (mSv/MBq)
Adrenals	1.60E-01	4.31E-02
Brain	3.82E-02	1.03E-02
Breasts	6.07E-02	1.64E-02
Gallbladder Wall	1.54E-01	4.15E-02
Lower Large Intestine	1.24E-01	3.36E-02
Small Intestine	1.38E-01	3.73E-02
Stomach Wall	1.47E-01	3.97E-02
Upper Large Intestine	1.21E-01	3.28E-02
Heart Wall	1.38E-01	3.74E-02
Kidneys	4.74E-01	1.28E-01
Liver	1.79E-01	4.84E-02
Lungs	3.43E-01	9.28E-02
Muscle	1.67E-01	4.51E-02
Ovaries	1.39E-01	3.74E-02
Pancreas	1.72E-01	4.65E-02
Red Marrow	1.00E-01	2.71E-02
Osteogenic Cells	1.47E-01	3.98E-02
Skin	6.19E-02	1.67E-02
Spleen	1.59E-01	4.30E-02
Testes	9.07E-02	2.45E-02
Thymus	1.23E-01	3.32E-02
Thyroid	1.14E-01	3.08E-02
Urinary Bladder Wall	1.29E-01	3.49E-02
Uterus	1.35E-01	3.66E-02
Total Body	1.34E-01	3.63E-02

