Based on the presented data, we have determined the kidneys to be dose limiting at 0.474 rem/mCi. In accordance with the guidance found in 21 CFR 361.1, 10.55 mCi may be administered to patients in this study.

Toxicology. The toxicology of cold $^{113}/^{115}\text{In}$ -XYIMSR-01 has been studied. Administration of $^{113}/^{115}\text{In}$ -XYIMSR-01 at doses of 11 and 55 $\mu\text{g}/\text{kg}$ was well tolerated by male and female Sprague-Dawley rats. No consistent or treatment-related effects were observed with respect to the following endpoints: survival; clinical signs; body weight; clinical chemistry, hematology,

IRB number: IRB00237314

Version: 3.0 Date: February 22, 2025

and urinalysis parameters; absolute or relative organ weights; or histopathology. These data support the safety of administering ^{111}In -XYIMSR-01 to human subjection.

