2. OBJECTIVES

2.1 Primary Objectives:

The primary objective of this study is to evaluate the safety, tolerability, and feasibility of ^{111}In -XYIMSR-01 SPECT/CT in patients with metastatic ccRCC.

2.2 Secondary Objectives:

- To determine the biodistribution and radiation dosimetry of ^{111}In -XYIMSR-01.
- To characterize the pharmacokinetics of ^{111}In -XYIMSR-01.
- To assess the concordance of findings on ^{111}In -XYIMSR-01 SPECT/CT with conventional imaging.

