⁷ SPECT/CT will be acquired at 2-4, 24± 1 hour, and 48± 1 hour post-injection. For the first three enrolled patients, a total of three fields of view will be acquired and for the remaining 7 patients two fields of view will be acquired. Each SPECT acquisition will be acquired over a 20-30 minute period.

⁸ A safety phone call will also occur 7(±3) days post-dosing. Ongoing adverse events thought to be related to ¹¹¹In-XYIMSR-01 will be followed until resolution of the adverse event, until an alternate cause has been identified, the patient is lost to follow-up, the patient withdraws consent, or it has been determined that ¹¹¹In-XYIMSR-01 is not the cause of the adverse event.

⁹ In order to minimize the need for research-only in-person visits, telemedicine visits may be substituted for in-person research study visits or portions of research study visits where determined to be appropriate and where determined by the investigator not to increase the participants' risks. Prior to initiating telemedicine for study visits the study team will explain to the participant, what a telemedicine visit entails and confirm that the study participant is in agreement and able to proceed with this method. Telemedicine acknowledgement will be obtained in accordance with the Guidance for Use of Telemedicine in Research. In the event telemedicine is not deemed feasible, the study visit will proceed as an in-person visit. Telemedicine visits will be conducted using HIPAA compliant method approved by the Health System and within licensing restrictions.

¹⁰ Safety blood tests: comprehensive metabolic panel to monitor blood chemistries, including kidney and liver function, and blood cell count will be collected at the end of 48 hour SPECT/CT imaging.

¹¹ A 12-lead electrocardiogram will be conducted at the end of 48 hour SPECT/CT imaging.

Pharmacokinetics & Imaging Timepoints:

Procedure	Pre-dose	0 hour	5± 2min.	10± 2 min.	20± 2 min.	30± 5 min.	60± 25 min.	90± 25 min.	2-4 hour	24± 1 hour	48± 1 hour
¹¹¹ In-XYIMSR-01 Administration		X									
Blood & Plasma Collection	X		X	X	X	X	X	X		X	
¹¹¹ In-XYIMSR-01 SPECT/CT Imaging									X	X	X

5. CRITERIA FOR DISCONTINUATION: CANCELLATION/WITHDRAWL PROCEDURES AND EARLY STOPPING RULES.

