7.2 Secondary Objectives

Biodistribution and Radiation Dosimetry: A secondary objective of this study is to determine the biodistribution and radiation dosimetry of ^{111}In -XYIMSR-01. To allow for this, SPECT/CT images will be acquired at 2-4, 24 ± 1 hour, and 48 ± 1 hour post-injection. For the first three patients a total of three fields of view will be acquired and for the remaining 7 patients two fields of view will be acquired. Each SPECT acquisition will be acquired over a 20-30 minute period. The first time point acquisition for each field of view will include a high resolution CT. All other time points will be acquired with a low-dose CT.

The acquired PECT/CT images will be used to perform the biodistribution and radiation dosimetry calculations. Time-activity curves (TACs) demonstrating radiotracer activity as a function of time post injection (minutes) will be drawn for the whole body and the following organs: brain, breast, gallbladder, stomach, pancreas, heart wall, lung, liver, bladder, muscle, pancreas, red marrow, spleen, adrenals, upper large intestine, lower large intestine, small intestine, thymus, thyroid, testes and ovaries. Individual organ residence times will be calculated by fitting an exponential function to the TAC data and analytically integrating the fitted functions from zero to infinity. Organ specific mean radiation-absorbed dose estimates for ^{111}In -XYIMSR-01 will be calculated from the individual organ residence times. Reference organ mass values will be adjusted based on actual organ masses. The OLINDA software package will be used to determine the absorbed dose [28].

Characterization of Pharmacokinetics: The pharmacokinetic profile of ^{111}In -XYIMSR-01 will be determined as a secondary endpoint of the study. ~5 mL of blood will be collected in heparinized tubes at pre-dose, 5 ± 2 minutes, 10 ± 2 minutes, 20 ± 5 minutes, 30 ± 5 minutes, 1 ± 0.25 hour, 1.5 ± 0.25 hour, and 24 hours ± 1 hour, post-injection to estimate elimination half-life. The collected blood will be evaluated for total radioractivity, the ratio of free versus protein-bound radiotracer, and measurement of the relative percentage of radiotracer and its metabolites.

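### The organ list for human time-activity curves omits the kidneys, the organ whose projected dose set the administered activity

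*Combined protocol and SAP*

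**What the plan says.** **Where the activity comes from.** The dosimetry part of section 1.1 tabulates organ doses projected for humans from preclinical biodistribution data ("we have estimated the human dosimetry for" this agent). It then concludes: "we have determined the kidneys to be dose limiting at 0.474 rem/mCi". With a reference to 21 CFR 361.1, it permits 10.55 mCi. Section 4 (footnote 6) and section 6.1.1 set the administered activity at 10.5±1 mCi.

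**What is to be measured in patients.** Section 2.2 makes human dosimetry a secondary objective: "To determine the biodistribution and radiation dosimetry of" the agent. Section 7.2 describes the analysis. Curves are drawn for the whole body and for these organs: "brain, breast, gallbladder, stomach, pancreas, heart wall, lung, liver, bladder, muscle, pancreas, red marrow, spleen, adrenals", followed by "upper large intestine, lower large intestine, small intestine, thymus, thyroid, testes and ovaries". Each organ's residence time comes from an exponential fit to its curve. Mean absorbed doses "will be calculated from the individual organ residence times", using OLINDA, and "Reference organ mass values will be adjusted based on actual organ masses".

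**What is imaged.** SPECT/CT is acquired at 2-4, 24 and 48 hours. The first three patients have three fields of view; "for the remaining 7 patients two fields of view will be acquired" (section 4, footnote 7, repeated in section 7.2). Neither section says where the fields are placed.

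**The concern.** The 0.474 rem/mCi coefficient is the one figure on which the administered activity rests, and it is a preclinical projection. A human dosimetry objective is the natural place to test it. The organ list does not include the organ to which it applies, and no other section plans a kidney curve, a kidney residence time or a kidney dose in patients. Elsewhere the kidney appears only as a comparator organ in the mouse data of section 1.1 and through renal function in eligibility and the safety laboratory tests.

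The omission does not look reasoned. The list includes brain, which has the lowest projected coefficient in the table (0.0382 rem/mCi), and leaves out the organ with the highest. At stake is whether the study can say, from patient data, if the projected kidney dose was right, both for this study's report and for any later use of the agent.

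**Working it through.** **Inputs**

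- Kidney coefficient 0.474 rem/mCi; lungs (next highest) 0.343; liver 0.179 (section 1.1 table).
- Permitted activity 10.55 mCi (section 1.1); administered 10.5±1 mCi (section 4, footnote 6).
- Organ list (section 7.2).
- Organ dose limit: not stated in the documents, so inferred below.

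**1. Reproduce the plan's activity.** Activity = organ dose limit / organ coefficient. Two limits were tried as assumptions:

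- 5 rem: 5 / 0.474 = 10.549 mCi, which matches 10.55.
- 3 rem: 3 / 0.474 = 6.33 mCi, which does not match.

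Conversely, 10.55 × 0.474 = 5.00 rem. The kidney coefficient with an implied 5 rem therefore accounts for the stated activity.

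**2. Check that no other organ could have set it.** Under the same implied 5 rem, lungs would allow 5 / 0.343 = 14.58 mCi and liver 5 / 0.179 = 27.93 mCi. Suppose a lower limit of 3 rem applied to the total body, red marrow and gonads (an assumption). Those would allow 3 / 0.134 = 22.39 (total body), 3 / 0.100 = 30.0 (red marrow), 3 / 0.139 = 21.58 (ovaries) and 3 / 0.0907 = 33.08 mCi (testes). None of these binds before the kidneys.

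**3. Compare the two organ lists.**

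- Section 1.1 table: 24 organs plus total body.
- Section 7.2 list: 14 + 7 = 21 entries, of which 20 are distinct because pancreas is repeated. All 20 are in the table.
- In the table but without a planned human curve: 24 − 20 = 4, namely kidneys, osteogenic cells, skin and uterus.

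**4. Follow the calculation chain.** In section 7.2 the curve gives the residence time, and the residence times give the dose. With no kidney curve there is no measured kidney residence time. The whole-body curve does not supply one, because it does not separate kidney activity from the rest.

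**5. Size.**

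| Quantity | As written | After the fix |
|---|---|---|
| Patients with a planned kidney curve | 0 of 10 | up to 10, at 3 time points each |
| Highest projected coefficient among organs with a planned curve | 0.343 (lungs) | 0.474 (kidneys) |
| Projected dose to that organ at 10.5 mCi | 10.5 × 0.343 = 3.60 rem | 10.5 × 0.474 = 4.98 rem |

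The unmeasured coefficient is 0.474 / 0.343 = 1.38 times the largest one that would be checked.

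**The case against.** Several points on the other side have force.

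- **It reads as a slip.** The repeated pancreas suggests that one entry was meant to be something else, and no rationale for leaving out the kidneys is given. That makes an omission more likely than a decision. It is still the text that an analyst would follow.
- **The kidneys will often be in view anyway.** Curves for adrenals, spleen, liver and pancreas need an upper-abdominal field, which would normally take in much or all of the kidneys. Images are archived (section 9.2), and nothing bars adding an organ later. This stands and lowers the risk. It does not remove it, because field positions are not stated and seven of the ten patients have only two fields.
- **No decision within the trial depends on it.** The activity is fixed, and the stopping rule in section 5.4 is based on toxicity. This also stands: the gap affects a secondary, descriptive output and later use of the agent, not the primary safety objective.
- **A strict field-placement rule has a price.** Forcing kidney coverage in every two-field patient could take fields away from chest or pelvic lesions and weaken the comparison with conventional imaging in section 7.2. Field length is not given, so the loss cannot be sized. The fix is worded accordingly.

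A reader might also infer that the study will report no kidney dose at all. The documents do not support that: section 7.2 limits which organs get curves, not which doses are reported, and OLINDA may still output a kidney figure. The difficulty is that such a figure would not rest on measured kidney uptake.

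**Conclusion.** The point holds as an omission in section 7.2. Following the list as it stands gives a measured kidney residence time in 0 of 10 patients, so the study could not confirm or correct the 0.474 rem/mCi that alone reproduces the 10.55 mCi activity. It should be corrected, but it does not threaten the primary objective.

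The conclusion rests on reading the section 7.2 list as complete, which is its plain sense. The link from coefficient to activity also rests on the back-calculated 5 rem. The omission itself does not depend on that figure.

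Two stronger readings are not supported. One is that the kidney dose in patients exceeds a limit: the documents contain no human kidney measurement, and the direction of any error in the projection is unknown. The other is that kidney dose could never be recovered: wherever the kidneys were imaged, a curve could be drawn later from the stored data.

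**What to change.** 1. In the section 7.2 organ list, replace the second pancreas entry with kidneys.
2. Report the measured human kidney dose in rem/mCi beside the projected 0.474, using the adjustment to actual organ mass that section 7.2 already plans.
3. In section 7.2 and section 4 (footnote 7), state that the upper-abdominal field already needed for adrenals, spleen, liver and pancreas includes the kidneys at 2-4, 24 and 48 hours. This should apply at least in the three patients with three fields, and in the two-field patients where lesion coverage allows.

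**Cost.** One more organ to contour at each time point, keeping any renal tumour out of the outline, and a minor constraint on field placement. No extra scan, visit or radiation is needed, and neither the activity nor eligibility changes.

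### The bladder's residence time is to come from an exponential through three scans, but bladder content fills and empties, so the fitted value can depend strongly on the time since the last void

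*Combined protocol and SAP*

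**What the plan says.** Section 7.2 (Biodistribution and Radiation Dosimetry) asks for time-activity curves for the whole body and a list of organs that includes the bladder: "heart wall, lung, liver, bladder, muscle, pancreas, red marrow". One method covers the whole list: "Individual organ residence times will be calculated by fitting an exponential function to the TAC data", with the fitted curve then integrated analytically to infinity. The data are three scans per patient: "SPECT/CT images will be acquired at 2-4, 24 ± 1 hour, and 48 ± 1 hour post-injection". Footnote 7 of the section 4 schedule gives the same times. On the dose step the plan says: "The OLINDA software package will be used to determine the absorbed dose". It names no voiding model and no void interval.

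The section 4 schedule has no record of void times and no timed urine collection. Urine appears only as screening urinalysis and as an option for the pregnancy test. On coverage, the first three patients have three fields of view, and "for the remaining 7 patients two fields of view will be acquired". The documents do not say whether either set covers the pelvis or the whole body.

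**The concern.** A solid organ takes up tracer and washes it out, so a smooth declining curve is a reasonable approximation. The bladder is a reservoir. Its content rises with urinary excretion and falls to near zero at each void, giving a saw-tooth. The residence time is the area under the saw-tooth, while a scan gives one height on one tooth. A smooth exponential through three such heights need not have the right area, and extra scans or exponential terms would not by themselves cure this.

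Two patients with the same excretion could therefore be given different bladder-wall doses because one emptied the bladder shortly before the first scan. Bladder-wall dose is among the organ doses that this objective is meant to estimate in humans, in place of the animal-based projection in section 1.1. Void times that are not recorded at the scan cannot be recovered later.

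**Working it through.** The plan states no bladder residence time, so there is no figure to reproduce. The check builds a known bladder curve, applies the planned rule, and compares the result with the true area.

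**From the documents:** scans at 2-4 h (3 h used here), 24 h and 48 h; one exponential per organ, integrated to infinity.

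**Assumed, not in the documents:** physical half-life 67.3 h; urinary fraction f = 0.5 (it multiplies both fitted and true values, so it cancels in the ratio); excretion half-time 3, 6 or 12 h; a void every 4 h; post-void residual 0, 5 or 10%.

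**Model with no residual.** With last void at time v (v = 0 if none since injection), content at time t is

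C(t) = f × [exp(−λv) − exp(−λt)] × exp(−μt), where λ = ln 2 / excretion half-time and μ = ln 2 / 67.3 = 0.0103 per h.

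The true residence time is the numerical area under C(t). The planned value is A/k from a fit of A·exp(−kt).

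**Worked case: half-time 3 h, no residual.** The 48-h content is negligible, so the least-squares fit is set almost entirely by the first two scans: k = ln(C3/C24)/21 and A = C3·exp(3k).

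- Full (no void since injection, next at 3.05 h, last before the 24-h scan at 23.05 h): C3 = 0.5 × (1 − 0.5) × 0.9696 = 0.2424; C24 = 0.000375; k = 0.308; A = 0.611; A/k = 1.98 h. Truth 0.945 h, ratio 2.10.
- Mid-cycle (voids at 1 h and 21 h): C3 = 0.5 × (0.7937 − 0.5) × 0.9696 = 0.1424; C24 = 0.00153; k = 0.216; A = 0.272; A/k = 1.26 h. Truth 0.911 h, ratio 1.38.
- Emptied 15 minutes before (voids at 2.75 h and 22.75 h): C3 = 0.5 × (0.5297 − 0.5) × 0.9696 = 0.0144; C24 = 0.00051; k = 0.159; A = 0.0232; A/k = 0.146 h. Truth 0.913 h, ratio 0.16.

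The truth moves between 0.91 and 0.95 h while the fitted value moves between 0.15 and 1.98 h.

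**All cases.** Fitted/true, as the range over residuals of 0, 5 and 10% and over least-squares and log-linear fitting:

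| Excretion half-time | Full at first scan | Mid-cycle | Emptied 15 min before |
|---|---|---|---|
| 3 h | 1.56-2.10 | 1.24-1.50 | 0.16-0.39 |
| 6 h | 1.21-1.48 | 1.20-1.33 | 0.23-0.38 |
| 12 h | 1.00-1.08 | 1.22-1.40 | 0.33-0.56 |

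**Second arrangement.** Here the gap since the last void is the same at every scan (4-h voids, 5% residual, log-linear fit, half-times 2 to 24 h). The ratio is 0.21-0.31 when the void was 15 minutes before each scan and 1.3-2.0 when it was 3 h before. At a 24-h half-time, some patterns with unequal gaps gave a rising curve with no finite integral.

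**Scale from section 1.1.** Bladder wall is projected at 0.129 rem/mCi, total body at 0.134 and kidneys at 0.474. At 10.5 mCi, bladder wall is 0.129 × 10.5 = 1.35 rem and kidneys 0.474 × 10.5 = 4.98 rem, a ratio of 3.7. The ratios in the table apply to residence time. They should not be multiplied onto 1.35 rem, because the documents do not say how much of that projection comes from bladder contents.

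**The case against.** The strongest reply is about scale. This is one organ in a descriptive secondary objective, and its projected dose is slightly below the total-body value and well below the kidneys. The primary safety endpoint, the sample size of 10, the stopping rule and the lesion comparison do not use it. All of that stands and limits the weight of the point. It does not remove the point, because the projection rests on animal data and the objective is there to obtain human values.

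A second reply is that the size rests on assumed kinetics. That also stands: the documents give no urinary fraction, excretion rate or void pattern.

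Two stronger readings are tempting, and neither is supported.

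- A reader might infer that the fitted value depends mainly on void timing. In simulation, void timing took about 57-81% of the log-variance, but only with an assumed 30% between-patient spread in kinetics and assumed random void times. The documents support no more than that it can depend strongly on void timing.
- A reader might quote the extreme case of complete emptying immediately before the first scan, where least-squares ratios of about 0.05 (3-h half-time) and 1.8 (12-h) can appear. These are artefacts of a zero residual and exact void placement. With a 5% residual they become about 0.14 and 0.53, and the second changes direction.

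A third reply is that the analyst could use a voiding model when running the dose software. Nothing in 7.2 says so, and the rule as written gives the bladder no exception.

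**Conclusion.** The point holds in a limited form. Applied as written, the section 7.2 rule does not estimate the area under a fill-and-void curve, and no other section supplies a bladder method or asks for void times. Under the assumptions listed, the fitted residence time is about 1.0-2.1 times the truth with the bladder full or mid-cycle at the first scan, and about 0.2-0.6 times when it was emptied 15 minutes earlier. The direction therefore depends on circumstances that the plan does not record.

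The ratios do not depend on the urinary fraction, but the absolute error does, and it is small if little activity is excreted in urine. The change is worth making before enrolment is complete. It is not a threat to the trial's main conclusions.

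**What to change.** In section 7.2:

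1. Take the bladder out of the exponential-fit rule and calculate its residence time with a fill-and-void (dynamic bladder) model. State the void interval used. This is a modelling assumption, not an instruction to patients.
2. Record the time of the last void before each scan, so that the measured bladder content can calibrate or check the model.
3. Estimate the excreted fraction from whole-body activity loss where coverage allows, meaning the three-field patients if those fields cover the body. Count decay-corrected loss from the injected activity to the first scan as well as between scans, since nothing is imaged before 2 h.
4. State that whole-body loss does not separate urinary from bowel excretion, and report the bladder-wall dose over a range of urinary fractions.

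The cost is a few sentences in 7.2 and one field on the scan form, with no added scans, samples or patients. The downside is that the bladder dose becomes conditional on the stated void interval and the assumed urinary fraction. Narrowing the urinary fraction itself might need timed urine collection, which this change does not require.

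### Organ residence times rest on an unbounded exponential through three scans: no finite answer if activity rises, too high for slow filling, usually too low for two-phase washout

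*Combined protocol and SAP*

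**What the plan says.** Section 7.2 (Biodistribution and Radiation Dosimetry) fixes the sampling: "SPECT/CT images will be acquired at 2-4, 24 ± 1 hour, and 48 ± 1 hour post-injection". Footnote 7 and the time-point table in Section 4 agree. Time-activity curves "demonstrating radiotracer activity as a function of time post injection (minutes) will be drawn for the whole body and the following organs", a list that includes gallbladder, stomach, bladder and the three bowel segments ("upper large intestine, lower large intestine, small intestine"). One rule for the residence time covers them all: "fitting an exponential function to the TAC data and analytically integrating the fitted functions from zero to infinity". The organ doses then "will be calculated from the individual organ residence times", using OLINDA.

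The section does not give the number of exponential terms, the fitting method, or whether the curves are decay-corrected. Nor does it give a lower limit on the fitted rate, the handling of the interval before the first scan, or what to do when a curve rises. Blood is sampled earlier, but for another stated purpose ("1.5 ± 0.25 hour, and 24 hours ± 1 hour, post-injection to estimate elimination half-life"), and no use of it in the organ curves is described. Coverage also varies: "For the first three patients a total of three fields of view will be acquired and for the remaining 7 patients two fields of view". Three points is therefore the most an organ can have, and only if it lies in a scanned field.

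**The concern.** One free exponential has two parameters, and two free exponentials have four. Three points therefore allow only the single-term reading, with one residual degree of freedom. A single exponential integrated to infinity suits an organ that is loaded early and clears at one rate. It does not suit an organ that gains activity between scans, or one that clears quickly and then slowly.

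Both shapes are foreseeable. Bowel, gallbladder and bladder can receive activity after the first scan, and Section 1.1 names the gastrointestinal tract, gallbladder and pancreatic ducts as normal tissues that express the target. For such curves the rule can return nothing usable, and the analyst would have to improvise after seeing the data.

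Residence times determine the organ doses, which Section 2.2 lists as a secondary objective. They would also be the human counterpart of the animal-based dosimetry table in Section 1.1. That last use is an inference, since the plan does not state it.

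**Working it through.** The plan gives no residence time, fit tolerance or extrapolated share, so there is no figure of its own to reproduce. The check applies the rule to noise-free curves with known integrals.

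**Inputs.** Scan times come from Section 7.2: first scan at 2, 3 or 4 h, then 24 and 48 h. Two inputs are assumed and not in the documents: a physical half-life of 67 h (range 60-75 h), so λ = ln 2/67 = 0.01035 per h, and all the organ kinetics.

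**Rule.** Fit A·exp(−kt). The integral is A/k if k > 0 and infinite otherwise. For scans at 3, 24 and 48 h the log-linear rate is k = (22 ln y₁ + ln y₂ − 23 ln y₃)/1014. It depends almost entirely on the first and last values.

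**1. Rising activity.** Take filling from zero with a 12 h uptake half-time, k_u = ln 2/12 = 0.05776. The curve is (1 − exp(−k_u t))·exp(−λt).
- Scan values: 0.154, 0.585, 0.571.
- True integral: 1/λ − 1/(λ + k_u) = 96.7 − 14.7 = 82.0.
- Fitted k = −0.028, so the prescribed integral is infinite.

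With uptake half-times of 3, 6, 12 and 24 h, first scans at 2, 3 and 4 h, and half-lives of 60, 67 and 75 h, 35 of 36 settings are infinite under both log-linear and nonlinear fitting. The exception (60 h half-life, first scan 4 h, uptake 3 h) is 18-19 times the truth.

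**2. Slower filling.** Over the 45 h between scans at 3 and 48 h, decay alone lowers activity by a factor 2^(45/67) = 1.59 (1.68 at 60 h, 1.52 at 75 h). If curves are not decay-corrected, uptake must grow by more than about this factor before the fit rises. Below it the answer is finite but too high. Take an organ starting at 1 and filling towards R with a 12 h half-time. The truth is R/λ − (R − 1)/(λ + k_u). For R = 1.3 (1.22-fold growth between 3 and 48 h):
- Truth: 125.7 − 4.4 = 121.3.
- Fit: 1.057/0.00594 = 178, a ratio of 1.47.

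For 1.08-fold growth the ratio is 1.11, and for 1.36-fold it is 2.2. If the curves are decay-corrected and integrated as written, every filling curve of this type that was run (R from 1.1 to 3) is infinite.

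**3. Two-phase washout.** The truth is f/(λ + ln 2/T_f) + (1 − f)/(λ + ln 2/T_s), where T_f and T_s are the fast and slow biological half-lives. First scan at 3 h:

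| Fast/slow share; T_f/T_s | Truth | Log-linear | Nonlinear |
|---|---|---|---|
| 60/40%; 4/60 h | 21.53 | 19.86 (−8%) | 18.14 (−16%) |
| 80/20%; 2/100 h | 13.82 | 11.93 (−14%) | 10.53 (−24%) |
| 90/10%; 3/200 h | 10.97 | 8.91 (−19%) | 7.92 (−28%) |

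For these curves 30-37% of the true integral lies after 48 h. Moving the first scan over 2-4 h gives −6% to −24% (log-linear) and −15% to −32% (nonlinear).

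A wider grid used 140 combinations: fast share 0.3-0.9, fast effective half-life 0.5-12 h, slow effective half-life 24-67 h. The fit was low in all of them with a first scan at 3 or 4 h. With a first scan at 2 h it was low in 93% (log-linear) or 99% (nonlinear). The lowest ratio was 0.56 and the highest 1.13.

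**4. A tail bounded at physical decay.** For the curve in step 1, with the first value held flat back to time zero:
- 0-3 h: 3 × 0.154 = 0.5.
- 3-24 h: 21 × 0.3695 = 7.8.
- 24-48 h: 24 × 0.578 = 13.9.
- Tail: 0.571/0.01035 = 55.2.

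The total is 77.3, which is 6% low, and 55.2/77.3 = 71% of it lies beyond 48 h. Across the 36 settings in step 1 the bounded method is 1-17% low, and always finite. On the washout curves it is 6-17% high with a first scan at 3 h, and 10-29% high at 2 h.

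**The case against.** The strongest reply has four parts.

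- **The plan does not prescribe the fit.** The 16-28% shortfall belongs to unweighted nonlinear least squares, which the first point dominates. A log-linear fit is equally consistent with the text and gives 8-19%. This stands, so both ranges are quoted.
- **The kinetics are assumed.** The mouse work summarised in Section 1.1 found activity retained only in tumour by 48 h, which argues against late filling and long tails in normal organs. It is the only kinetic evidence in the documents. It limits confidence in the size of the error, but human kinetics are what the study sets out to measure.
- **A trapezoid is not clearly better for washout.** With a first scan at 2 h it errs by +10% to +29%, against −6% to −13% for the log-linear fit, and its result depends on how the first hours are filled in. This stands, so it should not replace the fit for those curves.
- **Little depends on the result.** The objective is secondary and descriptive. The administered activity is fixed in Section 6.1.1, and the halting rule in Section 5.4 uses toxicity grade. This also stands.

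A constrained three-parameter uptake-and-clearance curve could be passed through three points, but it would leave no residual degree of freedom, and the plan does not name one. None of these replies supplies a rule for a rising curve.

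A reader might infer that every filling organ gives no answer, or that two-phase washout is always under-counted. Neither holds. Slow filling on uncorrected curves gives a finite, inflated value, and a few washout curves with a 2 h first scan are over-counted, by at most 13%.

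**Conclusion.** The concern holds in three parts. The prescribed integral is infinite when measured activity rises across the scans. It is too high when an organ fills more slowly than the label decays (1.11 to 2.2 times the truth for 1.08- to 1.36-fold growth). It is usually too low for two-phase washout, by about 8-19% (log-linear) or 16-28% (nonlinear) on the three curves with a first scan at 3 h.

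The first part follows from the stated rule for any curve whose fitted slope is not negative. The sizes rest on assumed kinetics, a 67 h half-life and noise-free values. Over half-lives of 60-75 h the nonlinear shortfall at 3 h runs from 14% to 31%.

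The documents do not support reading this as a threat to the primary safety objective or the sample size of 10, or as evidence that the trial's organ doses will be wrong by these amounts. It should be corrected because a foreseeable curve shape leaves a stated analysis without a usable result.

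**What to change.** In Section 7.2:

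1. State that the curves are not decay-corrected, or that physical decay is applied before integration. Name the fitting method.
2. Use the integral to infinity of the fitted exponential only when its rate is at least the physical decay rate of the label.
3. Otherwise integrate the observed points to 48 h, with a stated rule for time zero to the first scan. Add a tail that uses the slope of the last two points but is never slower than physical decay, and use physical decay alone if activity is still rising.
4. Report for each organ the share of the integral lying beyond 48 h.
5. For curves the exponential fits poorly, report the result with the same bounded tail as a sensitivity analysis, and define poor fit numerically in advance. Step 2 will not catch these curves: the washout fits at 3 h had rates 3.5 to 8.4 times physical decay (0.0361/0.01035 and 0.0870/0.01035).

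The cost is plan wording and minor analysis work, with no new scans. The downside is that a physical-decay tail overstates dose for organs that still clear after 48 h. The tail is too large by a factor 67/T when the true effective half-life after 48 h is T hours. The bounded method can also still be about 16% low for very slow filling (24 h uptake half-time).
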